### ***Consent Procedures:***

Written informed consent will be obtained from each subject after explaining the purpose of the study, description of experimental procedure (Ga Citrate PET/CT scan), and risk of radiation

exposure and other discomforts. The template of consent form is attached.

### **Recruitment Process:**

We plan to recruit subjects exclusively from Orthopedic clinic or Orthopedic Infectious Diseases Consult Service at NJMS. NJMS orthopedic surgeons and infectious disease specialists will be notified to screen for the subjects. They will be provided with the subject screening log template containing eligibility criteria and consent forms. Subjects will be pre-screened during the office visits by orthopedic surgeons and orthopedic infectious disease specialists.

Upon identifying eligible subjects, the principal investigator will be notified. Subject will be screened either by PI or Co-PIs. If all screening data are available and the subject is eligible for the study, informed consent will be obtained and documented. The PI/Co-PIs will notify the staff at the Advanced Practice Imaging Center and schedule the subject. The technologists will contact the supplier of investigational radiopharmaceutical compound, IBA molecular, and order the compound. The PI/Co-PIs will contact the subject with date and time of test visit and directions to imaging center.

### **Test Visit:**

Upon arrival to imaging center, the PI/Co-PIs will verify the subject's identity. The PI/Co-PIs will also verify that the consent form is signed.

### **Pre-imaging evaluation:**

Following information will be obtained and documented:

- Current symptoms:
- Vital Signs:
- Weight (kg)
- Height (cm)
- Blood Pressure
- Heart rate
- Respiratory rate
- Short physical examination
- Brief review of symptoms
- Pregnancy test (In women of child bearing age)

### **Image Acquisition Parameters:**

**Gallium PET/CT:**  $^{68}\text{Ga}$ -citrate will be synthesized according to the method described in the literature (28). IBA Molecular, a commercial radiopharmacy, will obtain a  $^{68}\text{Ge}/^{68}\text{Ga}$  generator that is produced by ITG Isotope Products. The IBA Molecular radiopharmacy will synthesize  $^{68}\text{Ga}$ -citrate and deliver to our facility in unit doses. Technologists will establish the intravenous access and the subject will receive 5 mCi of  $^{68}\text{Ga}$ -citrate intravenously. The subject will be placed in uptake room for 60 minutes to allow for optimal localization of investigational compound. Whole body PET/CT scan will be performed after 60 minutes of uptake phase.

Combined PET/CT imaging will be performed using the Discovery LS scanner (GE Medical Systems, Waukesha, WI). The CT scanner portion of the Discovery LS consists of a multi-detector helical CT (GE Lightspeed Plus, Waukesha, WI).

- Low dose CT scan will be performed followed by positron emission scan.
- CT imaging parameters will be as follows for a 6 to 7 bed position acquisition: 140 kVp, 80 mA, 0.8 s per CT rotation, pitch of 6, 22.5 mm/s table speed. CT thickness will be 5 mm.
- Positron emission data will be acquired for two sets of 6 positions, one starting from vertex to mid-thigh level and the second from pelvis to toes. Emission data will be acquired for 5 minutes for each bed position.
- PET images will be reconstructed using CT for attenuation correction with the ordered subset expectation maximization (OSEM) algorithm.

**FDG PET/CT:** Subjects will undergo FDG PET/CT scan using the same imaging parameters either on the same day or within the next 24-48 hours. The IBA Molecular radiopharmacy will synthesize F-FDG and deliver to our facility in unit doses. The subjects will be requested to fast for a minimum of 4 h prior to PET acquisition. After confirmation of a blood glucose level  $\leq$ 200 mg/dl, technologists will establish the intravenous access and the subject will receive approximately 10 mCi of F-FDG intravenously. The subject will be placed in uptake room for 60 minutes to allow for optimal localization of the compound. subjects will be requested to void prior to administration of 18FDG and again prior to image acquisition. Whole body PET/CT scan will be performed after 60 minutes of uptake phase using similar imaging parameters as described above.

### ***Post imaging evaluation:***

Upon completion of test procedure, PI/Co-PIs will evaluate the subject and obtain following data:

- Brief review of symptoms including signs of allergic reactions:
  - Rash
  - Itching
  - Difficulty in breathing
  - Swelling of tongue
- Blood Pressure
- Heart rate
- Respiratory rate
- Short physical examination, including assessment of injection site for swelling, redness, discharge and tenderness

### ***Follow-up:***

PI/Co-PIs will make a phone call to subject on following day of each scan and on 7th day after completion of test procedure and gather following information:

- Interval development of rash, itching, difficulty in breathing, swelling of tongue, fever, chills or any unusual symptoms
- Injection site for swelling, redness, discharge and tenderness

If subject experienced any of the above described signs or symptoms, PI/Co-PIs will schedule a follow-up visit with referring physicians (NJMS orthopedic surgeons).

***Data analysis:***

For each subject, we will record the presence and location of abnormal uptake on both Ga and FDG PET/CTs. We will then generate a region-of-interest around each area of morphologic abnormality to calculate a mean standardized uptake value (SUV), a maximum SUV, and a target-to-background ratio. These values will be compared with those of contralateral normal joint. Radiotracer uptake pattern on each modality will be classified according to known methods (29). Using the macroscopic intraoperative and later tissue histology and culture as the gold standard, sensitivity, specificity, and positive and negative predictive values of Ga and FDG PET will be calculated and compared with each other.

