**Study Title: Novel Gallium 68 Citrate Imaging in Orthopedic Infections.**

**Principal Investigator: [name]**

**Study Site: Rutgers New Jersey Medical School**

**1. Purpose/Specific Aims:**

The purpose of the current study is to demonstrate the feasibility and evaluate the accuracy of Gallium (Ga)-citrate positron emission tomography/computed tomography (PET/CT) in diagnosing prosthetic joint infection and compare it with fluorine-fluorodeoxyglucose-positron emission tomography/computed tomography (FDG-PET/CT). We expect that Ga-citrate PET/CT will serve as a novel molecular-based sensitive functional imaging modality superior to FDG-PET/CT. We intend to translate the results of this preliminary study to fuel larger studies in the utility of Ga-citrate PET/CT to evaluate prosthesis complications, where current available imaging techniques are challenging.

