#### ***Population characteristics:***

**Record Selections:** The following data will be obtained from the charts of the index cases:

1. Age
2. Gender
3. Race/ethnicity

4. Past Medical History
5. Past surgical history
6. Current medications
7. Prior medications
8. Weight, height and body mass index
9. History of alcohol abuse
10. History of intravenous drug use
11. Evidence of HIV infection (e.g. HIV RNA/DNA PCR, Western blot, viral load)
12. History of any other joint, connective tissue or systemic inflammatory diseases (e.g. systemic lupus erythematosus, sarcoidosis, amyloidosis)
13. Joint replacement postoperative course
14. White blood cell count
15. Erythrocyte sedimentation rate
16. C-reactive protein level
17. Histopathology for any biopsied joint/bone tissue
18. Pre and postoperative CT/MRI

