#### **4. Statistical Analysis:**

For each subject, we will record the presence and location of abnormal uptake. For the PET/CT images, we will generate a region-of-interest (ROI) around each area of morphologic abnormality to calculate a mean standardized uptake value (SUV), a maximum SUV, and a target-to-background ratio. A target-to-background ratio of at least 2.0 will be used to score a particular ROI as positive. These values will be compared quantitatively with those of contralateral normal joint. Radiotracer uptake pattern on each modality will be classified according to known methods (29). Then, we will descriptively and quantitatively correlate Ga-citrate PET/CT findings with those of F-FDG PET/CT. Using the macroscopic intraoperative and later tissue histology and culture as the gold standard, sensitivity, specificity, and positive and negative predictive values of Ga and FDG PET will be calculated and compared with each other. We will also review the PET/CT images for multifocal involvement, if any.

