#### **Statistical Analysis:**

Primarily, all variables will be analyzed and overall, descriptively, as follows:

- Mean, standard deviation, median and range for continuous variables
- Median, range and frequency distribution for discrete (ordinal) variations

- The results of the imaging modalities (PET, CT and MRI) will be classified as true positive (TP), true negative (TN), false positive (FP), or false negative (FN) according to the reference standard.
- The McNemar test of correlated properties will be used to statistically compare the imaging results of Ga-citrate and F-FDG PET with MRI and diagnostic CT.
- The student t-test will be used to statistically compare the quantitative findings of Ga-citrate and F-FDG scans.
- Analysis will be done on a lesion basis and on a patient basis.
- All P values, <0.05 will be considered significant.
- Cohen's k-statistic with 95% confidence intervals will be calculated to show the degree of association between the techniques.

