## **Statistical Analysis Plan:**

**Title of Study:** Novel Gallium 68 Citrate Imaging in Orthopedic Infections.

**Principal Investigator:** [name]

**NCT ID:** 20160000134

**Date:** 02/06/2018

The purpose of the study is to demonstrate the feasibility and evaluate the accuracy of 68Gallium (Ga)-citrate positron emission tomography/computed tomography (PET/CT) in diagnosing prosthetic joint infection and compare it with fluorine-fluorodeoxyglucose-positron emission tomography/computed tomography (FDG-PET/CT). We expect that Ga-citrate PET/CT will serve as a novel molecular-based sensitive functional imaging modality superior to FDG-PET/CT. We intend to translate the results of this preliminary study to fuel larger studies in the utility of Ga-citrate PET/CT to evaluate prosthesis complications, where current available imaging techniques are challenging.

For each subject, we will record the presence and location of abnormal uptake on both 67Gallium Citrate and Fluorodeoxyglucose PET/CT scans. We will then generate a region-of-interest around each area of morphologic abnormality to calculate a mean standardized uptake value (SUV), a maximum SUV, and a target-to-background ratio. These values will be compared with those of contralateral normal joint. Radiotracer uptake pattern on each modality will be classified according to known methods. Using the macroscopic intraoperative and later tissue histology and culture as the gold standard, sensitivity, specificity, and positive and negative predictive values of Ga and FDG PET will be calculated and compared with each other.

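### Neither the protocol nor the SAP requires the gallium and FDG scans to be read independently, masked to clinical and surgical findings, or locked before the reference result is known

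*Protocol*

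**What the plan says.** The reading plan is short. Protocol section 3, *Data analysis*, states "For each subject, we will record the presence and location of abnormal uptake on both Ga and FDG PET/CTs". The SAP has the matching sentence, "For each subject, we will record the presence and location of abnormal uptake on both 67Gallium Citrate and Fluorodeoxyglucose PET/CT scans" (the isotope label there is a separate matter). The next step is "We will then generate a region-of-interest around each area of morphologic abnormality to calculate a mean standardized uptake value (SUV", together with a maximum SUV and a target-to-background ratio. Protocol section 4 and the SAP add a numeric rule, "A target-to-background ratio of at least 2.0 will be used to score a particular ROI as positive", and both have uptake patterns classified by a published method.

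The calls are then set against operative findings, histology and culture. Sensitivity, specificity and predictive values of the two tracers are compared, and "Cohen's k-statistic with 95% confidence intervals will be calculated to show the degree of association between the techniques".

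Other sections bear on who may know what:

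- The principal investigator and co-investigators screen subjects (*Recruitment Process*), and raised ESR and CRP are entry criteria.
- They also see subjects after each scan: "Upon completion of test procedure, PI/Co-PIs will evaluate the subject and obtain following data".
- The chart data collected for the study include ESR, CRP, CT/MRI from before and after the operation, and "Histopathology for any biopsied joint/bone tissue".
- Section 1 states in advance that Ga is expected to be a "sensitive functional imaging modality superior to FDG-PET/CT".

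Neither document says who reads the scans, how many readers there are, whether the two tracers are read separately, what a reader may see, or when a call becomes final.

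**The concern.** This is a paired accuracy study in which both index tests are interpreted by people. Three routes of review bias are left open.

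1. **One tracer informs the other.** If a doubtful focus on one scan is resolved by looking at the paired scan, the two calls are drawn together. Kappa rises, and the discordant pairs that carry the Ga-FDG contrast become fewer.
2. **Clinical or reference information informs the read.** A call made with operative, histology or culture results in view will tend to agree with them, which flatters both tracers.
3. **Expectation informs the read.** With superiority of Ga expected in advance, borderline calls may tilt towards Ga.

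These routes do not all push the same way, so the net direction is unknown and no analysis of the recorded calls can correct it. The accuracy estimates are meant to support funding and larger studies, so they should be protected from it.

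**Working it through.** The plan gives no figure to reproduce: the 17 subjects come without power, effect size or expected rates. The check is mainly one of text, followed by labelled illustrations.

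**Step 1. Safeguards looked for in both documents**

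| Safeguard | What the documents give |
|---|---|
| Identity and number of readers | Not stated; the text uses only the first person plural |
| Ga read separate from FDG read | Not stated |
| Masking to ESR/CRP, examination, other imaging | Not stated |
| Masking to operative, histology or culture results | Not stated |
| Calls final before the reference result | Not stated; scans precede surgery by up to 4 weeks (section 3 and *Imaging Protocol*), but the time of reading is open |
| Numeric positivity rule | Yes: target-to-background ratio of at least 2.0 |
| Definition of the background region | Not stated |

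The only mention of blinding is in the title of a cited study in the bibliography.

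**Step 2. How much discretion the ratio rule leaves.** Ratio = target SUV / background SUV. Take an assumed target SUV of 4.0:

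- background 1.9: 4.0 / 1.9 = 2.11, positive;
- background 2.1: 4.0 / 2.1 = 1.90, negative.

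A small shift in an undefined background changes the call. The choice of abnormality, the placement of the region and the pattern class are further judgements.

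**Step 3. Weight of one call on accuracy.** One changed call moves sensitivity (infected group) or specificity (aseptic group) by 1/m, where m is the size of that group. The split of the 17 is not given, so m is assumed:

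- m = 5: 1/5 = 20 percentage points;
- m = 9: 1/9 = 11 points;
- m = 12: 1/12 = 8 points.

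**Step 4. Direction of the effect on kappa.** Invented table of 17: 8 both positive, 6 FDG-positive and Ga-negative, 0 the reverse, 3 both negative. Kappa = (po − pe) / (1 − pe).

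- po = 11/17 = 187/289; pe = (14×8 + 3×9)/289 = 139/289; kappa = 48/150 = 0.320.
- One Ga call moved to agree with FDG: po = 12/17 = 204/289; pe = (14×9 + 3×8)/289 = 150/289; kappa = 54/139 = 0.388.

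Agreement rises, as expected. The shift is small beside the asymptotic 95% interval for the first table, about 0.00 to 0.64.

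**The case against.** The strongest reply is that silence is not evidence of bad practice, and that the plan has safeguards. Positivity is scored by a numeric cut-off, regions are tied to a morphologic abnormality, and both scans are acquired before surgery. Every subject has raised ESR and CRP and a swollen, painful joint by eligibility, so only the degree can influence a reader. The post-imaging evaluation is mostly a safety check. The study is a pilot with a primarily descriptive analysis.

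Much of this stands. The clinical-data route is weaker than the other two, and the cut-off does narrow discretion. It does not close it (step 2), and acquiring scans before surgery does not stop them being read afterwards.

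Three stronger readings are tempting and should be resisted.

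- **That the scans are read side by side by an unmasked team.** The wording says that each scan is recorded, not that the two are viewed together. Lack of a masking rule does not show that readers will be unmasked.
- **That the readers are the people who examine subjects and abstract histopathology.** No reader or abstractor is identified, and *Chart Review Process* lists a separate data manager.
- **That one influenced read would overturn a significant Ga-FDG result.** Take the invented table in step 4 and an exact two-sided McNemar test, p = 2 × 0.5^n for n discordant pairs all in one direction. Six pairs give 0.031 and five give 0.063. But six is the only such count at which moving one call to agreement crosses 0.05: seven pairs give 0.016 and drop only to 0.031, and five or fewer never reach significance. The table ignores disease status. The plan also assigns McNemar to comparing the PET scans with MRI and diagnostic CT, so a Ga-FDG McNemar test is not clearly planned.

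**Conclusion.** The point holds as an omission with consequences. A team could follow both documents to the letter and still read one tracer with the other in view, or read either after the surgical result is known. That leaves the central Ga-FDG accuracy comparison and kappa open to review bias.

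The documents do not show that such bias will occur, and its size and direction cannot be derived from them. The figures of 20, 11 and 8 points show only how much one call weighs. They rest on assumed group sizes of 5, 9 and 12 and are not estimates of bias. This should be corrected because the remedy is cheap and the sample is small. It does not invalidate the design.

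**What to change.** Add a reading procedure to the protocol and SAP, using the existing readers:

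- De-identify the scans. Read all Ga scans in one session and all FDG scans in another, each in its own random order, with a stated interval between sessions.
- Withhold the paired scan, clinical and laboratory data, and other imaging reports. Where the team allows, assign reads to members who neither examined the subject nor abstracted the chart.
- Define one ROI rule and one background region, and apply both identically to the two tracers. A single-tracer session reveals which tracer is being read, so this rule is the main guard against expectation.
- Time-stamp and lock each call, ROI value and pattern class in REDCap before operative, histology and culture results are opened to the reader. With batched reading some results will already exist; the requirement is that the reader has not seen them.
- Keep any clinical or safety read separate, and do not use it as accuracy data.
- Let the masked read cover the full acquired field. Limiting it to the pelvis-to-toes set would mask nothing, and could miss the other orthopedic hardware that the *Subjects* paragraph allows.

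If reading has already begun, available images can be re-read under these rules by someone unaware of the outcomes.

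The cost is protocol and SAP wording, a lock in a database already in use, a second reading session and some delay before the research read. No extra scan, subject or reader is needed.

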***Chart Review Process:***

Electronic databases: PACS, EPIC, Logician (Electronic Medical Database of university hospital, affiliate of Rutgers New Jersey Medical School)

Data Manager: [name]

Data management service: RedCap

**Protected Health Information will be only stored in RedCap. We do not plan to store PHI on personal or mobile devices such as laptops and memory sticks.**

***Coded Identifier List:*** DOB, MRN, name, dates of services

The file with the link between personal identifiers and the data will be kept for 6 years.

***Data Collection Form:*** Attached

***Risks of Harm:***

This research study involves exposure to radiation emitted by the injected radioactive metal (Gallium citrate), injected radioactive glucose (fluorine-fluorodeoxyglucose) and the X-rays delivered by the CT scan.

The Human-use subcommittee and full Radiation Safety Committee of Rutgers New Jersey Medical School reviewed the dosimetry calculations of Ga Citrate and F FDG based on ICRP Report # 53 (30) and utilized updated tissue weighting factors published in ICRP Report # 103 (31) to arrive at effective doses (See attached PDF document titled: Dosimetry). Accordingly, from 5 mCi of Ga Citrate injection, female effective dose was calculated at 3.95 mSv and male effective dose was 3.89 mSv and from 10 mCi injection of F FDG, female effective dose was calculated at 5.82 mSv and male effective dose was 5.71 mSv. The study total per annum equivalent doses and effective doses per research subject were found to be within FDA diagnostic limits as attached. Accordingly, the effective dose is a measure of radiation exposure that is used for calculation of risk. The unit of the effective dose is the millisievert (mSv). The average person in the United States of America receives an effective dose of about 3 mSv per year from naturally occurring radioactive materials

and cosmic radiation from outer space. These natural background radiation doses vary throughout the country. In New Jersey, radon gas is the largest source of natural background radiation. Americans also receive radiation exposures from man-made sources such as medical procedures and consumer products. The USA average exposure from all sources is about 6.2 mSv per year.

From the participation in the study while undergoing (no. of scans = 2) scans and radionuclide injections (no. of injections = 2):

- Total effective dose is calculated at 15.1 mSv for women and 14.9 mSv for men.
- Total dose to the critical organ, small intestine from injection of  $^{68}\text{Ga}$ -citrate is calculated at 21.6 mSv.
- Total dose to the critical organ, urinary bladder wall, from injection of  $^{18}\text{F}$  FDG, is calculated at 29.9 mSv.

As a result of each Gallium PET/CT scan:

- Effective dose to the women is calculated at 6.61 mSv; that is 3.95 mSv from radiation emitted by the radiogallium injected for the PET scan and 2.66 mSv from X-rays used in the CT scan.
- Effective dose to the men is calculated at 6.55 mSv; that is 3.89 mSv from radiation emitted by the radiogallium injected for the PET scan and 2.66 mSv from X-rays used in the CT scan.

As a result of F18-FDG PET/CT scan:

- Effective dose to the women is calculated at 8.48 mSv; that is 5.82 mSv from radiation emitted by the FDG injected for the PET scan and 2.66 mSv from X-rays used in the CT scan.
- Effective dose to the men is calculated at 8.37 mSv; that is 5.71 mSv from radiation emitted by the FDG injected for the PET scan and 2.66 mSv from X-rays used in the CT scan.

The risk associated with this level of radiation exposure is too small to be measured and is small when compared with other everyday risks. It is well below the limit of 50 mSv per study that is allowed by the US Food and Drug Administration for experimental studies in humans. It is also well below the limit of 50 mSv per year that can be received by US radiation workers.

Theoretically, radiation exposure can damage sperm and eggs. About 2000 mSv is required to cause temporary sterility in humans. The dose to the testes and ovaries from participation in this study is calculated at approximately 11.8 mSv and 13.3 mSv respectively, about 500 times lower than the dose that can cause permanent sterility. The scientists who studied the survivors of the atomic bomb in Japan did not demonstrate any increased genetic or reproductive effects in the next generation. However, experimentally we know that the ova ovulated in the first few cycles after an exposure to radiation have a higher risk of a genetic effect. The recommendations of the Health Physics Society (<http://www.hps.org>) for the women who have received radiation therapy are to wait for three cycles before they attempt to get pregnant. While participating in the study, the subjects will undergo PET/CT scan of the whole body and will have exposure far less than someone who is receiving radiation therapy to the abdomen and are not anticipated to be at higher risk of radiation exposure to the egg or sperm that could result in birth defects.

After undergoing PET scan, the subjects will be instructed to drink plenty of water and void frequently for the remainder of the day. They will be also instructed to not to have a close contact with pregnant women, babies and young children for at least 6 hours after their scan.

It is possible, but unlikely, that the Gallium citrate/F-FDG injection will miss the vein. Though there is no subjective data available for such an event, there is a theoretical likelihood of developing skin cancer at the injection site from local radiation.

Unlikely non-radiation related risks from PET/CT scans include:

- Discomfort from lying still on the enclosed scanning table
- Bruising or bleeding at the site of injection of radiotracer
- Infection at the site of injection
- An allergic type or other adverse reaction to the Gallium citrate or F-FDG

